Umbilical cord tissue (UCT) is less well defined. However, as reported in NCT02176317, the safety and tolerability profile of autologous CB infusion in ASD was excellent. No serious adverse events were reported, and adverse events, in general, were sparse. Three children had mild allergic reactions associated temporally with the infusions, consisting of cough and hives during infusion for 1 child and cough post-infusion for 2 children. Also, one child was noted to be more irritable for 2 days post-infusion. No subjects discontinued prematurely from the study due to adverse events.

Lipoaspirate is obtained via liposuction, or the removal of adipose tissue via a suction method, is a common cosmetic procedure performed by plastic surgeons. Depending on the liposuction location and indication, 100cc to 2,000cc of lipoaspirate can be safely removed from a subject during a single liposuction procedure. Through a tissue process which includes washing and centrifuging, the cellular components can be extracted as a cell pellet, which is also known as Stromal Vascular Fraction (SVF). This cellular product is thought to contain adipose tissue-derived stem cells as well as leukocytes, erythrocytes and other cell types. However, numerous pre-clinical studies that have analyzed SVF have shown that it contains a heterogeneous cell population, thus, making its precise cellular components unclear. Furthermore, the fate of these cellular components can vary significantly; the age of the adipose tissue donor, the type and localization of the adipose tissue, and cellular isolation process may affect the cellular analysis outcome.

Adipose tissue has been found to have a large amount of mesenchymal stem cells versus that in bone marrow. These cells are currently being used in a variety of clinical research studies within the regenerative medicine field. The cellular pellet, SVF, can be easily maintained and expanded in culture, showing stable growth and proliferation rates [8].

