In order to accurately assess the efficacy of these treatments, routine follow-up examinations will be necessary. Follow-up exams will occur at intervals of 1 week, 1 month, 3 months, 6 months, 9 months (telephone only) and 1 year. After completing the screening and consent portion of the trial, the subjects will undergo a pre-injection MRI and then an additional MRI at 6 and 12 months. Additionally, subjects will fill out PROs at each time point.

The Marcus Center for Therapeutic Cell Characterization and Manufacturing (MC3M) at Georgia Institute of Technology will serve as a core cell analytics center for this clinical trial. MC3M's goal is to provide deep and broad characterization of all cells used in the trial, including synovial fluid, harmonize and standardize analytical and processing parameters across the different clinical sites and eventually, as patient outcome data become available, the MC3M will apply quantitative advanced modeling tools to identify predictive signatures of cell properties that correlate with efficacy and safety.

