### 8.1.2 Treatment Visit (Visit 2, Day 0)

- Collect concomitant medications
- Focused knee assessment (if required, at the discretion of the treating investigator)
- Perform vital signs
- Assess adverse events
- Perform pregnancy test (on female subjects of childbearing potential)
- Confirm subject eligibility
- Study procedures (**depending on subject randomization**)
  1. Arm 1-BMAC Treatment: bone marrow aspiration, cell processing and product release criteria testing
  2. Arm 1-CSI Treatment: bone marrow aspiration, cell processing, product release criteria testing and CSI preparation
  3. Arm 2-SVF Treatment: lipoaspirate procedure, cell processing, and product release criteria testing
  4. Arm 2-CSI Treatment: lipoaspirate procedure, cell processing, product release criteria testing and CSI preparation
  5. Arm 3-UCT Treatment: dispense UCT-MSCs, dose preparation, and product release criteria testing
  6. Arm 3-CSI Treatment: CSI preparation
- Perform arthrocentesis and knee injection
- Process and store samples for cell characterization (details are described in the Laboratory Manual)
- Home physical therapy program to begin post procedure day 8, see Appendix 12.1. Instructions for at home physical therapy will be provided to the subject by the study staff.

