### **8.1.9 Unscheduled Visits**

Unscheduled visits are allowed as needed and at the discretion of the treating investigator for more frequent follow-up than what is required in the protocol. The treating investigator will determine the appropriate assessments to be conducted during this visit based on the reason for the Unscheduled Visit. Data from the Unscheduled visits will be captured in the EDC.

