### **9.3.3 Efficacy Analyses across Subgroups**

The heterogeneity of treatment effects across age, sex, and ethnicity will be evaluated using a statistical test for interaction terms. Specifically, effects of treatment in subgroups will be determined by including the additional interaction terms between treatment and the three subgroups (age, sex, and ethnicity) in the repeated measures model described above for the eight efficacy variables.

The following variables will be treated as categorical variables in all of the linear mixed models.

- Treatment arms: CSI (reference), BMAC, ADP, UCT
- Age:  $\leq 65$  (reference) vs.  $>65$
- Sex: female vs male (reference)

- Ethnicity: Hispanic vs non-Hispanic
- Time: 0, 1, 2, 3, 4, 5 representing baseline and 1, 3, 6, 9 and 12 months follow-up visits

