#### 9.4.4 Analysis of Adverse Events

Additionally, the following AE-related specific analysis will be performed.

1. Frequency and percentages of each event will be summarized by treatment arm for the following:

- AEs
  - AE in relationship to study treatment (not-related, possibly related, or related)
  - AE Severity
  - SAEs
  - SAE in relationship to study treatment (not-related, possibly related or related)
  - SAE Severity
  - Any Laboratory Toxicities
2. Allergic reaction and infection will be summarized as one category and corresponding number and proportions will be provided for each CTCAE grade level by treatment arm. These AEs will be counted only once per subject as the most severe level (i.e., maximum severity) reported across the six study assessments/visits during the 1-year follow-up period and compared between treatment arms with a chi-square or Fisher's exact test. The 95% confidence intervals will also be provided for the proportions.
  3. Estimates of infection at harvest site or treated/targeted knee by treatment arms and time on study will be estimated and compared by performing a generalized estimating equations (GEE) analysis of the repeated binary responses within participant. The subjects will be clustered within center. This analysis will be implemented via the SAS GENMOD Procedure, using an exchangeable correlation structure for the repeated data within subjects (binomial-logit model). Infection rates and 95% confidence intervals will be used to summarize the data by treatment group and clinical visit.
  4. Subjects who become pregnant while on the study will be followed for AEs/SAEs that may occur for up to 30 days following the birth of the child.

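### The pooled infection and allergic-reaction comparison (section 9.4.4, item 2) is worded more narrowly than the adverse events collected, and allergic reaction has no between-arm comparison of its own

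*Combined protocol and SAP*

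**What the plan says.** Section 9.4.4 item 2 sets two rules for one safety comparison.

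- **Pooling.** "Allergic reaction and infection will be summarized as one category", shown by CTCAE grade and arm with 95% confidence intervals, and compared with a chi-square or Fisher's exact test.
- **Counting.** Each subject counts once, at the maximum severity "reported across the six study assessments/visits during the 1-year follow-up period and compared between treatment arms". The six are not listed.

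Other parts of the document bear on these rules:

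- Section 4.1 lists the follow-up contacts: "Follow-up exams will occur at intervals of 1 week, 1 month, 3 months, 6 months, 9 months (telephone only) and 1 year".
- Section 8.1.2 includes "Assess adverse events" among the Day 0 tasks, and the Schedule of Activities marks adverse event monitoring at Day 0 and at unscheduled visits. Section 8.1.9 adds: "Data from the Unscheduled visits will be captured in the EDC".
- Section 8.4.3 sets collection of adverse events from signed consent to the one-year visit.
- Section 9.4.4 item 3 compares infection at the harvest site or treated knee between arms with a GEE model, summarised by treatment group and clinical visit.
- Section 9.4.2 and section 9.4.4 item 1 tabulate adverse events by arm, with no visit limit and no between-arm test.

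**The concern.** Two features of item 2 could weaken what it shows.

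First, harvest and injection both take place on Day 0, and Day 0 is not a follow-up visit. An immediate reaction to the injected product would be recorded that day. The only timing evidence in the document, on cord-blood infusion in section 2.2, points the same way: "Three children had mild allergic reactions associated temporally with the infusions". A programmer who applies the six-visit wording literally would leave such events out of the count. A programmer who reads it as shorthand for the whole year would include them. The plan does not settle which table is right.

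Second, UCT is the only allogeneic product and its recipients have no harvest, while BMAC and SVF recipients do. If allergic reaction were more frequent in one group and infection in another, the pooled proportions could look alike. For infection, item 3 supplies a separate comparison. For allergic reaction the plan has none.

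**Working it through.** **1. The plan's own figure.** Item 2 has no stated power. The only calculated figures for this pooled category are the lower limits in Table 1 of section 9.4.3. The two-sided 95% Wilson score limit (z = 1.96) reproduces all 12 rows after rounding; for example, 7/30 gives 11.79%, printed as 12%. Table 1 serves the stopping rule and does not define item 2's window.

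**2. Which six visits?** Two sets of six can be found.

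| Set | Members | Includes Day 0? | Includes unscheduled visits? |
|---|---|---|---|
| Follow-up contacts (section 4.1, Schedule of Activities) | Days 7, 30, 90, 180, 270, 365 | No | No |
| Efficacy time points (section 9.3.3) | "Time: 0, 1, 2, 3, 4, 5 representing baseline and 1, 3, 6, 9 and 12 months follow-up visits" | No (PROs are scheduled at screening, not Day 0) | No |

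The second set also omits Day 7. Adverse events are monitored at 8 scheduled points (screening, Day 0 and 6 follow-up contacts) and at unscheduled visits. Either literal reading is therefore narrower than the data collected.

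**3. Masking in the composite.** Group size is 4 sites × 30 = 120 (section 9.2). The counts are assumed: 7 infections and no allergic reactions in one arm, the reverse in the other.

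- Composite: 7/120 v 7/120, two-sided Fisher p = 1.
- One component: 7/120 v 0/120, p = 2 × C(120,7)/C(240,7) = 0.0143.

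Exact cancellation is not required. Section 6.2.2 gives 10 CSI subjects per arm per site, so 4 × 10 = 40 per arm. CSI subjects in Arms 1 and 2 are harvested, which makes 80 of 120 CSI subjects against none of the UCT recipients. With an assumed 8 allergic reactions in UCT and 6 infections in CSI, the composite is 8/120 v 6/120 (p = 0.78), while allergic reaction alone is 8/120 v 0/120 (p = 0.007).

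**4. Range of assumed rates.** The document gives only bands of 1–10%. Take mirror-image risks in two arms of 120, two-sided alpha 0.05 (assumed), and a merged rate of 1 − (1 − high)(1 − low). At 10% and 1% this is 1 − 0.90 × 0.99 = 10.9% in both arms.

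| High v low | Fisher power, one event alone | Merged rate, both arms | Merged test rejects |
|---|---|---|---|
| 10% v 1% | 0.86 | 10.9% | 2.9% |
| 8% v 1% | 0.68 | 8.9% | 2.7% |
| 5% v 1% | 0.28 | 6.0% | 2.3% |

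For a four-arm chi-square test, assume infection at 10% in BMAC and SVF, 1% in UCT and (2 × 10% + 1%)/3 = 7% in CSI, with allergic reaction at 10% in UCT and 1% elsewhere. Simulated power is 0.87 for infection alone, 0.97 for allergic reaction alone and 0.10 merged. With 5% in place of 10%, the figures are 0.29, 0.54 and 0.07.

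**5. Effect of the window, literal reading only.** Assume allergic reaction 10% v 1%, infection 1% in both arms, and a share f of allergic reactions recorded only outside the six visits.

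| f | 0 | 0.25 | 0.5 | 0.75 | 1 |
|---|---|---|---|---|---|
| Merged Fisher power | 0.76 | 0.56 | 0.30 | 0.08 | 0.001 |

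The document gives no value for f.

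**The case against.** The strongest reply is that safety reporting does not depend on item 2. Infection has its own between-arm analysis in item 3. Sections 9.4.2 and 9.4.4 item 1 show the events by arm without a visit limit, and the stopping rule in section 9.4.3 uses the same pooled category under continuous monitoring. This stands. A reader might infer that Day 0 reactions and unscheduled-visit infections disappear from the safety results, or that item 2 is the only test of harm from harvest or from the allogeneic product. The document supports neither inference.

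It can also be said that the six-visit wording is loose rather than restrictive. Section 8.4.4 has events followed at later contacts, so an infection first seen at an unscheduled visit could be recorded again at the next scheduled one. Injection and harvest sites are inspected at Days 7 and 30, both among the six. This largely answers the point for infection. It answers less for a brief reaction on Day 0. Item 3 also reports by clinical visit, so the same question about the window arises there.

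Nor do the risks split cleanly by arm. Section 2.3.1 lists infection for knee injection in every arm and allergic reaction for the steroid. The cord-blood evidence comes from intravenous infusion of a different product in children, and section 2.3.1 states that no risks of UCT cells injected in the knee have been reported. The 7 v 7 example is therefore a constructed worst case and not a forecast.

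Finally, separate tests on rare events add multiplicity. That is a real cost, and labelling handles it. None of these replies supplies a between-arm comparison of allergic reaction.

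**Conclusion.** The point holds in a limited form. Item 2 states a counting window that, taken literally, is narrower than the adverse events collected. The omission is clear for Day 0 and only possible for unscheduled visits. Allergic reaction is tested between arms solely within a composite in which an opposite infection difference can mask it.

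The possible size ranges from nothing to a complete loss of the signal in that one test. If the two risks do not run in opposite directions and the window is read broadly, little changes. Under mirror-image risks of 10% and 1%, power of 0.86 for a single event becomes a 2.9% rejection rate for the composite. These figures rest on assumed rates within the 1–10% bands and an assumed alpha of 0.05; the loss from the window also depends on an unknown f. They show what the rule allows and do not predict what the trial will find. Because the terms are collected and tabulated separately, the matter can be repaired in full before analysis.

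**What to change.** Amend section 9.4.4 item 2 in two places, and carry the same wording into any fuller analysis plan.

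1. **Window.** Replace the reference to six visits with a rule based on onset: count every event that starts between the beginning of the Day 0 procedure and the Month 12 visit, wherever it was reported, including Day 0 and unscheduled visits.
2. **Components.** Beside the composite, give allergic reaction and infection their own table by CTCAE grade and arm, with 95% confidence intervals and a Fisher's exact test. Label these as descriptive and not adjusted for multiplicity.

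The cost is a wording change and two more safety tables, with no new data, visits or change to the stopping rule. The downside is two further sets of unadjusted tests on rare events, so an isolated small p-value should be read alongside the counts and intervals.

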### **6.2.2 Implementation of Randomization and Blinding**

Subjects randomized to Arm 1 or Arm 2 will undergo a procedure (bone marrow aspiration or liposuction) but will only receive one of the possible injections. For instance, subjects randomized to the control portion of Arm 1 will undergo a bone marrow aspiration but will receive a blinded corticosteroid injection. The bone marrow aspirate will still be processed and used to help quantify cell characteristics. Subjects randomized to Arm 3 will not undergo the procedures mentioned above. They will be blinded and receive either the stem cell injection or the corticosteroid injection.

Four hundred eighty subjects will be randomly assigned to treatment in this multicenter trial. Subjects at each clinical site will be randomized to ensure the trial is single-blind with a 1:1 allocation ratio across the four treatment groups.

One hundred twenty subjects will be randomized at each of 4 clinical sites. Arm 1: Forty subjects will be randomized with a 3:1 allocation ratio (bone marrow derived MSCs versus corticosteroid injection; 30:10). This same implementation plan will be used to randomize 40 subjects to Arm 2 (adipose derived MSCs versus corticosteroid injection) with a 3:1 allocation ratio and to randomize 40 subjects to Arm 3 (umbilical cord tissue MSCs versus corticosteroid injection) with a 3:1 allocation ratio.

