#### **9.2 Sample Size Determination**

The total estimated sample size for the proposed intention-to treat, parallel-group, multicenter, randomized, controlled trial is 480 subjects. The primary endpoints are Visual Analog Scale (VAS) pain score and the pain subsection of the Knee Injury and Osteoarthritis Outcomes (KOOS). The sample size calculations are based on improvements (from baseline to 1-year) in the visual analog scale (VAS) pain score and total KOOS. Total KOOS was used as a proxy and should ensure that the study is amply powered.

Assuming a decline of 1 point on average in pain in the Control arm (corticosteroids) and a decline on average of 2.5 points in a treatment arm (mesenchymal stem cells) and an estimated standard deviation on change of 3.5, the proposed sample sizes (n=121 subjects

per group or 484 total subjects) will provide 91% power to detect a difference on change of 1.5 points at the two-sided 5% significance level if the true difference between treatment groups is 1.5 points (two-sided two-sample equal variance t-test).

Assuming an increase of 10 points on average in total KOOS in the Control arm (corticosteroids) and an increase on average of 20 points in a treatment arm (mesenchymal stem cells) and an estimated standard deviation on change of 20, the proposed sample sizes (n=121 subjects per group or 484 total subjects) will provide 97% power to detect a difference on change of 10 points at the two-sided 5% significance level if the true difference between treatment groups is 10 points (two-sided two-sample equal variance t-test).

Each of the four participating sites will accrue 30 subjects to each of the 4 treatment groups. Cohort retention is expected to be 90% at 1-year.

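### The infection GEE promises group-by-visit intervals that, with arm-by-visit terms, will almost certainly not all exist, on a composite outcome that is not like for like between groups

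*Combined protocol and SAP*

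**What the plan says.** Section 9.4.4 item 3 defines the outcome and the comparison: "Estimates of infection at harvest site or treated/targeted knee by treatment arms and time on study will be estimated and compared". The method is a "generalized estimating equations (GEE) analysis of the repeated binary responses within participant", run in SAS GENMOD, "using an exchangeable correlation structure for the repeated data within subjects (binomial-logit model"). Between these statements stands: "The subjects will be clustered within center". The promised output is: "Infection rates and 95% confidence intervals will be used to summarize the data by treatment group and clinical visit".

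The item lists no model terms, does not name the GEE cluster outright, and gives no expected infection rate, no correction for few clusters and no fallback for sparse data.

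The size of the problem follows from other places:

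- Section 9.4.4 item 2 counts events "reported across the six study assessments/visits during the 1-year follow-up period".
- Section 9.2: "Each of the four participating sites will accrue 30 subjects to each of the 4 treatment groups".
- Section 6.2.2 sends the control subjects of Arms 1 and 2 through the harvest for blinding, but "Subjects randomized to Arm 3 will not undergo the procedures mentioned above".
- The notes to the Schedule of Activities have the harvest site inspected at days 7 and 30 only.
- Section 2.3.1 lists infection in its 1-10% band, separately for bone marrow aspiration, liposuction, knee injection and steroid injection.

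**The concern.** Three features of item 3 work against each other.

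First, infection should be uncommon, and the plan divides it into four groups by six visits. A logit model with a separate parameter for each cell has no finite estimate where a cell has no event.

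Second, the outcome joins knee and harvest-site infection, but exposure to a harvest differs between groups. A difference between groups can therefore come from the harvest rather than from the injected product.

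Third, in a GEE the cluster unit determines the robust variance. The item points to the subject twice and to the centre once, so a programmer could follow either.

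At stake is the only planned between-group test of infection on its own. Item 2 tests infection and allergic reaction as one category, and Section 9.4.2 tabulates by preferred term without a test.

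**Working it through.** **The plan's own figures.** Item 3 states none. The nearest are the Wilson lower limits in Table 1 of Section 9.4.3, where infection is part of the monitored event. All 12 reproduce to the whole percent (for example 3/10 gives 10.78%, printed 11%; 6/30 gives 9.51%, printed 10%).

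**Inputs.** Four sites × 30 = 120 subjects per group. Four groups × six visits = 24 cells. One-year risk *p* is taken as 1%, 2%, 5% and 10%. The band is the protocol's, but applying it to the composite, and the timing of events, are assumptions.

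**Empty cells, even timing.** P(cell empty) = (1 − *p*/6)^120, and the expected number empty is 24 times that. At 5%: (1 − 0.00833)^120 = 0.366, and 24 × 0.366 = 8.8. At 10%: (1 − 0.01667)^120 = 0.133, giving 3.2; P(no cell empty) = (1 − 0.133)^24 ≈ 0.03. The early-weighted column assumes that events fall 50/30/8/4/4/4% over the six visits. The last column is 1 − [1 − (1 − *p*)^120]^4.

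| One-year risk | Events per group | Empty cells of 24, even | Empty cells, early-weighted | P(at least one group has no infection at all) |
|---|---|---|---|---|
| 1% | 1.2 | 19.7 | 20.1 | 0.76 |
| 2% | 2.4 | 16.1 | 17.3 | 0.31 |
| 5% | 6.0 | 8.8 | 12.8 | 0.01 |
| 10% | 12.0 | 3.2 | 9.1 | <0.001 |

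With even timing, the probability of at least one empty cell exceeds 0.999 at 1-5% and is 0.97 at 10%. These results do not depend on the cluster unit.

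**Cluster unit.** A simulation under the null (2,000 runs per rate) used an arm + visit logit model, Wald tests at 5%, an independence working correlation as a simplification, and no true centre or subject correlation.

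| One-year risk | Model estimable | Single contrast, centre as cluster | 3-df arm test, centre | Single contrast, subject as cluster | 3-df arm test, subject |
|---|---|---|---|---|---|
| about 1.8% | 18% | 13% | 57% | 0.3% | 0.9% |
| about 6% | 95% | 17% | 68% | 2.9% | 3.0% |
| about 17% | 100% | 17% | 68% | 4.4% | 4.8% |

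Rejection rates are among estimable runs. A separate two-group simulation (120 per group, four centres, 20,000 runs) gave 16% at 5% incidence and 18% at 10% with centre as cluster. With four centre clusters the middle matrix of the robust covariance has rank 3, against 24 parameters in an arm-by-visit model, so a 15-df interaction test cannot be formed. With 480 subject clusters it has full rank, 24 of 24.

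**Composite outcome.** CSI subjects number 40 in each of Arms 1, 2 and 3, so 40 + 40 = 80 of 120 have a harvest. All BMAC and SVF subjects have one; no UCT subject does. Suppose knee infection risk is equal in every group and harvest-site risk is *h*, ignoring overlap. The composite in CSI then exceeds that in UCT by (80/120) × *h*. With *h* at 1% and 10%, the ends of the listed band, this is 0.7 and 6.7 percentage points with no product effect.

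**The case against.** The strongest reply is that item 3 is being read too harshly. Several points stand.

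- **Cluster.** A reader might infer that centre is the GEE cluster and that the tests are therefore invalid. The text does not settle this. Two of its three statements make the subject the correlated unit, and the third can mean only that subjects are nested in centres. The inflated error rates hold only on the centre reading.
- **Structural zeros.** A reader might call the empty cells structural because UCT subjects have no harvest site. For the composite that is wrong: every group receives a knee injection, so the empty cells are sampling zeros. The term fits only a separate analysis of harvest-site infection.
- **Model terms.** An arm-by-visit interaction is implied by the promised output but not written. Rates by visit could be descriptive, and an arm + visit model is usually estimable at about 6% risk. It is often not estimable near 2%, however, and no fallback is given.
- **Extent.** It would be too strong to say that most cells will be empty. With even timing that is true at 1-2%, not at 5-10%.
- **Role.** This is not the main infection comparison. It is one of several additional safety analyses. Section 9.4.2 tabulates infections by subject, and the stopping rule in Section 9.4.3 uses subject-level Wilson limits.
- **Strategy comparison.** Comparing infection from the whole intervention, harvest included, is a legitimate safety question. But the CSI harvests are done for blinding, so the CSI composite does not describe a steroid injection alone.
- **Separate SAP.** Section 9.3 says a SAP has been developed. The public text gives only the protocol's statistical section, so the cluster unit or a fallback may be specified there.

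**Conclusion.** The concern holds in a limited form. If arm-by-visit terms are fitted, some promised logit intervals will almost certainly not exist, whichever cluster is used: about 20, 16, 9 and 3 empty cells of 24 are expected at 1%, 2%, 5% and 10%. This rests on an assumed one-year risk for the composite and even timing; early-weighted timing is worse at every rate. The composite outcome can also produce a UCT-CSI difference that reflects the blinding harvest rather than the product.

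The cluster wording is ambiguous. It does harm only if centre is used, when a single contrast has about 13 to 18% type I error. The documents do not support saying that the analysis is invalid as written. The matter is confined to a supplementary safety analysis, but it deserves correction because no other planned between-group test covers infection alone.

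**What to change.** Rewrite Section 9.4.4 item 3, and the SAP to match:

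1. Compare the proportion of subjects ever infected by treatment group, with exact 95% intervals and Fisher's exact test. This remains computable with no events: for 0/120 the exact upper limit is 1 − 0.025^(1/120) = 3.0%.
2. Report knee infection in all four groups. Report harvest-site infection only among subjects who had that harvest: bone marrow in Arm 1 and lipoaspirate in Arm 2, each with 120 treated and 40 CSI subjects.
3. Give rates by visit descriptively.
4. If a GEE is kept, state the subject as the cluster, site as a fixed effect and no arm-by-visit interaction, and pre-specify a fallback for sparse data, such as the analysis in step 1 or a Firth-penalised model.

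The cost is a change of wording. No new data are needed, provided the adverse event record identifies the infected site, which should be confirmed. The downside is that visit-level infection rates become descriptive.
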